### **Study Tasks:**

#### Affective Touch Task

This task will be administered while subjects are in the scanner. In this task, touch will be administered using a 5 cm wide goat hair brush applied to a 9cm section of the forearm. Brush will be used rather than hand touching (i.e. skin-to-skin contact) to control for variation in skin temperature (Ackerley et al, 2014). We will use a hand-held brush, as previous reports indicate no difference in ratings of tactile stimulation delivered manually versus a force-controlled robot (Triscoli et al, 2013). Participants will be instructed to look straight ahead at a fixation cross presented on the screen throughout the brushing trials to avoid providing any visual cues regarding touch administration. The experimenter will wear headphones to receive metronomic audio cues for consistency in brushing velocity. The task consists of four blocks of 8 trials each, four at each velocity, 3 cm/s ("slow") and 30 cm/s ("fast"), with velocity order within each block pseudorandomized but not repeated more than 3 times. Ratings of "pleasantness," "intensity," and "desire to experience that type of touch again," will be conducted during intertrial intervals using a 7-point Likert scale ranging from 1 (i.e. extremely unpleasant) to 7 (i.e. extremely pleasant). A 1-2 sec variable inter-trial interval (ITI) will separate each rating, with the

final rating followed by a 7- 9 sec variable ITI before the next trial begins. The primary behavioral ratings in this task are the ratings of pleasantness of the brushing.

### **Neuroimaging:**

Imaging will be performed using a state-of-the-art Phillips Achieva Quasar Dual 16 Ch 3T MRI scanner. Three BOLD echo-planar imaging (EPI) scans will be acquired to measure responses to the tasks (gradient echo, 193 volumes; repetition time, 2,000 ms; echo time, 29 ms; flip angle, 76°; 35 interleaved 3mm-thick axial slices; matrix, 88×88; 2.5×2.5×3.0 mm^3 voxels; acceleration factor 2; and 3D prospective acquisition correction algorithm). Structural scans will also be acquired using a T1-weighted magnetization-prepared rapid gradient echo (MPRAGE) sequence for co-registration and normalization to the Montreal Neurological Institute (MNI) coordinate system. Head movement will be minimized through detailed instructions to participants and a conformal pillow which is fitted to the participant's head using a vacuum pump to withdraw air from the pillow. Participants are told to immediately alert the MRI technicians if they experience any discomfort or feel unwell, in which case the scan will be stopped and the participant removed from the scanner. The entire scan should require 45 minutes to complete.

### **Data Analysis**

Subjects will be grouped according to ASQ scores in three groups; low (0-10), medium (10-20), and high (20-32), which will be used as a between-subjects factor in the analysis. The subjective and mood effects of the drug will be assessed using a repeated measures analysis of variance (ANOVA) with AQ (low, medium, high) as a between-subjects factor, and dose (placebo or MDMA) and time as within-subjects factors. Imaging data will be compared within subjects across MDMA and placebo conditions. For data pre-processing we will combine realignment algorithms (MCFLIRT), locally written code, and normalization procedures from Statistical Parametric Mapping software (SPM8; Wellcome Trust Center for Neuroimaging, London). Strict quality control procedures will be in place to evaluate movement (excluding subjects > 2mm translation, and 1 degrees rotation in re-alignment parameters) and ensure proper normalization to the MNI152 template. Functional data will be processed and analyzed using conventional methods implemented with SPM8, previously described in our papers (Gorka et al., 2013; Wardle et al., 2014a). Statistical analysis will use the general framework of the modified General Linear Model implemented in SPM8 in combination with a temporal convolution model for event-related analyses in a random effects model. Statistical inference will use random field theory to account for non-independent observations within a smooth map, providing corrected probabilities. Given hypotheses about specific brain regions, small volume corrections will be applied to provide appropriate levels of stringent controls to hypothesis testing. We will implement 2 complementary approaches to test regional activation: 1) hypothesis-driven anatomically-focused region of interest (ROI)-based analysis of the primary contrast of interest; and 2) whole-brain voxel-wise 'search' of activation not constrained to ROIs related to these same factors. We will use repeated-measures ANOVAs to assess significant effects of drug (placebo versus MDMA) on each of the two brush velocities for the touch task (slow vs. fast) and the social interaction task (self vs. other). Change scores will be computed for ratings of pleasantness of affective touch (MDMA-placebo). Oxytocin levels and subjective ratings will be compared with ANOVAs with ASQ (low, medium, high) as a between-subjects factor, and dose (placebo or MDMA) as a within subjects factor.

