
### **Procedure**

Orientation: Participants who meet criteria will first be scheduled for an orientation session. During this session, subjects will be informed that the capsules used in the study may contain a placebo, stimulant, a sedative/tranquilizer, or a cannabinoid/marijuana-like drug. This range of drug types is included to minimize expectancy effects. Participants will be given an oral description of the study procedures and the written consent form. After the experimenter reviews this information and the consent form with the subject, and answers any questions he/she may have, subjects will sign the informed consent document. Abstention from recent drug and alcohol use will be verified by breathalyzer and urine drug tests. Subjects will be asked about possible claustrophobia, and they will complete the scanning questionnaire to ensure that they have no metal implants.

Study Sessions: Two 4.5-hour sessions will be conducted, separated by at least 72 hours. Please see below for a full timeline of the study sessions. On study session days, participants will arrive at 9am, and complete a urine and breath screening for recent alcohol and drug use, and a pregnancy test (for women). Participants will then complete Time 1 measures of subjective mood and drug effects, and complete these same measures periodically throughout the study (see below). Participants will ingest the capsule at 9:30am. For the next hour, while the drug is absorbed, they will be allowed to relax and watch a movie or read a book, but will not be allowed to do work. Subjects will be escorted to the MRIRC at 10:30am to undergo an fMRI scan while performing the Touch Task. The scan will last approximately 45 minutes. Participants

will then be escorted back to the lab, where they will remain, completing subjective measures of the drug effect every hour until at least 1:30pm (when we expect drug effects will end), or until the effects of the drug return to baseline (as measured by both subjective report and cardiovascular variables).

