#### Timeline

9:00 am – Participant arrival, drug, alcohol and pregnancy testing, snack provided  
9:15 am – Time 1 Measures – POMS, DEQ, VAS, Blood Pressure, HR  
9:30 am – Administration of capsule  
10:00 am – Time 2 Measures - POMS, DEQ, VAS, Blood Pressure, HR  
10:30 am – Time 3 Measures - POMS, DEQ, VAS, Blood Pressure, HR  
11:00 am – fMRI scan with Touch Task  
11:45 am - end of scan  
12:30 pm – Time 4 Measures – POMS, DEQ, VAS, Blood Pressure, HR  
1:00 pm - Time 5 Measures – POMS, DEQ, VAS, Blood Pressure, HR  
1:30 pm - Participant leaves lab

End of study phone call: After the subject's last session we will conduct an end-of-study interview by phone. Participants will be asked to indicate how much they liked each study drug and how much they would want to take each drug again. Participants will also be asked to report which type or types of drugs they think they received at each session. Finally, participants will be told the study hypotheses, methods and the types of drugs that they received, and will be given a chance to ask any final questions.

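### The mood and subjective-effects ANOVA gives the pre-dose reading no baseline role; if all five readings are levels of time, the dose main-effect estimate is four fifths of the mean post-dose effect

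*Combined protocol and SAP*

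**What the plan says.** The Data Analysis section assigns subjective and mood effects to a repeated-measures ANOVA with AQ group between subjects and "dose (placebo or MDMA) and time as within-subjects factors". It does not list the levels of time, say which term is the test of interest, or name a baseline term. The only change score it defines is MDMA minus placebo for touch pleasantness, which is not a change from the pre-dose reading. A later sentence describes a second analysis with no time factor: "Oxytocin levels and subjective ratings will be compared with ANOVAs with ASQ (low, medium, high) as a between-subjects factor", with dose within subjects.

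The Timeline schedules five labelled readings per session. The first is "9:15 am – Time 1 Measures – POMS, DEQ, VAS, Blood Pressure, HR", followed by "9:30 am – Administration of capsule". Times 2, 3 and 4 are at 10:00, 10:30 and 12:30, and the last is "1:00 pm - Time 5 Measures – POMS, DEQ, VAS, Blood Pressure, HR". The Procedure section confirms that the pre-dose and later instruments are the same: "Participants will then complete Time 1 measures of subjective mood and drug effects, and complete these same measures periodically throughout the study". It describes the readings after the scan differently, as "completing subjective measures of the drug effect every hour until at least 1:30pm", which does not match 12:30 and 1:00.

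**The concern.** Order is randomised and Time 1 precedes the capsule, so the expected MDMA-minus-placebo difference at Time 1 is zero. A dose main effect that averages over all five readings therefore averages in a known zero. At the same time, the session-to-session difference in starting mood, which is measured, stays in the error term. What is at stake is precision, and a drug-effect estimate that does not answer the obvious question of how large the effect is after dosing. The dose-by-time interaction is the other place to look for the effect. However, it is an omnibus test over 4 degrees of freedom and is not aimed at a sustained post-dose difference. It also relies on sphericity across unevenly spaced times, and the section names no correction.

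**Working it through.** **The plan's own figure first.** The Subjects section gives d=0.44, N=45 and power above 80%, for touch pleasantness. A paired t-test, two-sided at 0.05 (alpha is not stated, so this is an assumption), gives 82.3%. The figure reproduces. The documents give no power figure or effect size for mood.

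**Effect on the estimate.** Let m be the mean MDMA-minus-placebo difference over the four post-dose readings. With five equally weighted levels the dose main effect is (0 + 4m)/5 = 0.80m.

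**Effect on the standardised effect.** Assume unit variance and a common correlation r between the MDMA-minus-placebo differences at different times.
- Variance of the four-reading mean: v4 = (1+3r)/4.
- Variance of the five-reading mean: v5 = (1+4r)/5.
- Ratio of standardised effects: 0.8 × √(v4/v5). This is 0.894 at r=0 and 0.802 at r=0.9, a loss of 10.6% to 19.8%.

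**Illustrative power.** Set the standardised effect of the post-dose mean to 0.44, so m = 0.44√v4, with N=45.
- Five-level main effect: d = 0.8m/√v5.
- Post-dose mean with the Time 1 difference as covariate: d = m/√(v4 − r²).
- Dose-by-time, flat post-dose effect: noncentrality = 45 × 0.8m²/(1−r), on 4 and 4 × (45−3) = 168 degrees of freedom. The factor 0.8 is the sum of squares of the profile (0,1,1,1,1) about its mean.

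At r=0.4, for example: v4 = 0.55, v5 = 0.52 and m = 0.326. The five-level d is 0.8 × 0.326/√0.52 = 0.362. The adjusted d is 0.326/√(0.55−0.16) = 0.52. The noncentrality is 45 × 0.8 × 0.326²/0.6 = 6.4.

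| r | Main effect, five levels | Dose-by-time, flat effect | Times 2–5 only | Times 2–5 with Time 1 covariate |
|---|---|---|---|---|
| 0.2 | 68% | 27% | 82% | 86% |
| 0.4 | 66% | 49% | 82% | 93% |
| 0.6 | 65% | 80% | 82% | 98.5% |

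These figures ignore the few degrees of freedom spent on the covariate and the ASQ factor. At r=0 the covariate gains nothing (82.3%).

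**Sphericity.** If correlation decays exponentially with a constant of 60 to 240 minutes (assumed), simulation of the uncorrected dose-by-time F at the Timeline's five times gives a type I error of 6.7% to 9.0%. On Times 2 to 5 alone it is 6.6% to 8.7%, so dropping Time 1 does not cure this.

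**The case against.** The strongest reply is that the plan never says Time 1 is a level of time, and never names the dose main effect as the test. Both points are correct. Inclusion of Time 1 is an inference from the labels Time 1 to Time 5. A dose-by-time ANOVA would ordinarily include the interaction, which contains the contrast of post-dose readings with Time 1. A reader might infer that the pre-dose reading is wasted altogether; the documents do not support that. The interaction is not always weak either. With a rise-and-fall profile of the same mean (assumed weights 0.4, 1.4, 1.3, 0.9) its power is 47%, 76% and 97% at r = 0.2, 0.4 and 0.6. For a flat effect, though, it stays below the baseline-adjusted contrast throughout that range, and the plan does not choose it.

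The second reply is that d=0.44 belongs to touch pleasantness. The Subjective Measures section presents the POMS and the VAS items as sensitive to drug effects, so mood effects may be larger. At d=0.6 the five-level main effect has 89% to 91% power, and at d=0.8 about 99%. The power loss could then be immaterial, although the estimate would still be 0.80 of the post-dose mean.

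Third, a reader might infer that every repeated outcome loses power. The Data Analysis section states no model for blood pressure or heart rate. The DEQ asks about a felt drug effect, so its pre-dose values may vary little and adjustment may gain little.

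If Time 1 is not a level of time, the dilution disappears, but the collected baseline then has no stated use.

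**Conclusion.** The point holds as an improvement to a secondary analysis. The plan gives Time 1 no baseline role. On the natural but unstated reading that time has five levels, the dose main-effect estimate is exactly 4/5 of the mean post-dose effect, with a standardised loss of 11% to 20%. The power figures (65% to 68% as read, 82% for post-dose readings only, 86% to 98.5% with adjustment) are illustrations. They rest on a borrowed effect size, two-sided alpha of 0.05, equal variances and a common correlation of 0.2 to 0.6, none of which the documents give for mood.

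A reader might also infer that the trial's stated power is reduced. It is not. The Affective Touch Task section makes pleasantness its primary behavioural rating. That rating is collected in the scanner with no pre-dose value, and the sample size was set on it.

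**What to change.** For the secondary mood and subjective measures, make the dose contrast the mean of Times 2 to 5, adjusted for Time 1, and keep ASQ and dose-by-ASQ in the model. In this crossover the adjustment should use the MDMA-minus-placebo Time 1 difference as covariate, or the session baseline split into within-subject and between-subject parts, so that differences between people are not mixed with differences between sessions. A covariate is safer than a simple change from Time 1: under the same assumptions the change score has 25% power at r=0 and 57% at r=0.3, and only matches the unadjusted post-dose mean (82%) at r=0.5.

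Test dose-by-time separately, with a Greenhouse-Geisser correction or an unstructured covariance. Moving to a mixed model without naming a covariance structure would not remove the sphericity problem. In the same edit, reconcile the reading times in the Procedure and Timeline sections, and say which of the two descriptions of the subjective-ratings analysis applies.

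The cost is analysis wording only. The Time 1 readings are already scheduled, so no visit, measure or participant is added.

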fMRI studies indicate that individuals with autistic symptoms exhibit reduced responsiveness to affective touch in the orbitofrontal cortex (OFC) and superior temporal sulcus (STS), and individuals with diagnoses of ASD show reduced activity in these regions as well as in the bilateral insula and other regions involved in social and emotional processing (Voos et al. 2012, Kaiser et al. 2015). To understand the mechanism by which MDMA increases reactivity to affective touch, we will use functional magnetic resonance imaging to test the effects of the drug on BOLD responses to affective touch in individuals with a range of autistic traits. We hypothesize that individuals with high scores on the ASQ will exhibit reduced OFC, STS, and insular responses to affective touch, and that MDMA will enhance touch-related activity in these regions, correcting these deficits.

**Specific Aim 3: To determine the mediating role of oxytocin in the effects of MDMA on responses to affective touch in individuals with a range of autistic traits**

MDMA has been shown to increase plasma oxytocin, raising the possibility that oxytocin mediates the enhancement of social behavior induced by MDMA. Here we propose to assess whether the MDMA-induced rise in plasma oxytocin predicts enhanced responses to affective touch.

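### Small volume correction covers only the volume and contrast searched; the plan states no error control across the three regions and two velocities of Aim 2

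*Combined protocol and SAP*

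**What the plan says.** Specific Aim 2 (Background and Specific Aims) predicts that people with high ASQ scores "will exhibit reduced OFC, STS, and insular responses to affective touch", and that "MDMA will enhance touch-related activity in these regions". That makes three hypothesised regions.

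Data Analysis then sets out the imaging inference:

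- Error control: "Statistical inference will use random field theory to account for non-independent observations within a smooth map, providing corrected probabilities", and, for the hypothesised regions, "small volume corrections will be applied to provide appropriate levels of stringent controls to hypothesis testing".
- Two approaches: a "hypothesis-driven anatomically-focused region of interest (ROI)-based analysis of the primary contrast of interest", and a "whole-brain voxel-wise 'search' of activation not constrained to ROIs related to these same factors".
- The tests: repeated-measures ANOVAs for "effects of drug (placebo versus MDMA) on each of the two brush velocities".

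The section gives no significance level. It does not say whether each region has its own search volume or the three share one mask. It does not say which contrast is primary, or how many regions or velocities must be positive for Aim 2 to be supported. It states no adjustment across regions or velocities.

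**The concern.** Random field theory with a small volume correction controls the chance of a false positive among the voxels of one search volume, for one contrast. It does nothing across separate volumes or separate contrasts. A plan with three regions and two velocities can therefore apply it correctly every time and still have a family-wise error well above the nominal level for the claim that MDMA enhances touch-related activity in these regions.

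Aim 2 carries the mechanistic claim of the study. With the primary contrast undefined, the region and velocity to emphasise can be chosen after the data are seen. A single positive result could then be reported as confirmation, under a statement that control was stringent.

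**Working it through.** **Inputs**

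- Regions: 3 (OFC, STS, insula), from Specific Aim 2.
- Velocities: 2 (slow, fast), from Data Analysis.
- Drug tests if each region is tested separately at each velocity: 3 × 2 = 6.
- Alpha per test: not stated. I assume two-sided 0.05 after small volume correction.
- Correlation between tests: not stated. All tests use the same participants and scans, so positive correlation is likely. I show 0.3 to 0.7.
- Decision rule: not stated. I assume that any positive test is read as support for Aim 2.

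**The plan's own figure.** The only statistical design figure is under Methods, Subjects: more than 80% power with 45 participants and d = 0.44. A paired t-test at two-sided 0.05 has noncentrality 0.44 × √45 = 2.95 on 44 degrees of freedom, which gives power of 82.3%. The figure reproduces. It concerns pleasantness ratings; the plan gives no error rate or power for imaging.

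**Family-wise error.** Under independence, FWER = 1 − (1 − 0.05)^k. Under any dependence it is at most k × 0.05.

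- Six tests: 1 − 0.95^6 = 0.265; at most 0.30.
- Three regions, one contrast: 1 − 0.95^3 = 0.143; at most 0.15.
- One combined mask, two velocities: 1 − 0.95^2 = 0.0975; at most 0.10.

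For positive correlation I simulated k equally correlated standard normal statistics, one million draws per setting, and counted draws with any |z| above 1.96.

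| Layout | Independent | 0.3 | 0.5 | 0.7 |
|---|---|---|---|---|
| 3 regions × 2 velocities (6 tests) | 26.5% | 24% | 21% | 16% |
| 3 regions, one contrast (3 tests) | 14% | 14% | 13% | 11% |
| Combined mask, 2 velocities (2 tests) | 9.8% | 9.5% | 9.1% | 8.4% |

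At correlation 0.9 the six-test figure is still about 11%. It falls to 5% only if the tests are fully dependent.

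**With adjustment.** A Bonferroni first step over six tests uses 0.05/6 = 0.0083, and 1 − (1 − 0.0083)^6 = 4.9% under independence. Over three tests it uses 0.05/3 = 0.0167, and 1 − (1 − 0.0167)^3 = 4.9%. Positive correlation lowers both. Holm uses the same first step.

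**Cost in power, for illustration.** The documents give no imaging effect size. If a region's effect were also d = 0.44 with n = 45, the same noncentral t calculation gives 82% at 0.05, 68% at 0.0167 and 58% at 0.0083. These last two figures assume that the region has to pass the strictest Holm step.

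**The case against.** The strongest reply is that this is a gap in specification, and that the inflation is not shown. Several parts of that reply stand.

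- **Combined mask.** The plural in the correction sentence leans towards separate volumes but does not settle it. One mask over all three regions fits the text, and then only the velocities multiply.
- **Primary contrast.** The plan does refer to one, in the singular. Once defined, it could bring the family below six.
- **ANOVA wording.** The repeated-measures ANOVAs could be read as one drug-by-velocity model per region. With one test per region, the three-test row applies.
- **Decision rule.** Aim 2 is worded jointly for the three regions. If all three must be positive on one contrast, testing three regions does not inflate the error of that claim. A reader might infer that one positive region is enough, but the plan states neither rule.
- **Whole-brain search.** It is not uncontrolled: random field theory is specified, and the search is kept apart from the hypothesis-driven analysis.
- **Outside sources.** The section points to the group's published methods. Masks and thresholds may be defined there, which cannot be checked here.

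A reader might also count left and right regions separately and arrive at twelve tests. The documents do not support that: both sides of the insula are mentioned only when earlier findings are described, and no test by hemisphere is planned.

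None of this supplies the missing statement. Each reply is a choice that the plan could have made and did not write down. Even the combined mask leaves about 8% to 10% when both velocities are tested and either counts. The six-test count also leaves out the ASQ-group effects that Aim 2 predicts and the social interaction task named in the same ANOVA sentence.

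**Conclusion.** The point holds as an unsupported claim of control. Small volume correction does not deliver stringent control for Aim 2 as a whole, because nothing in the plan controls error across regions or velocities, and the alpha, search volume and primary contrast are left open.

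The size is conditional on two-sided 0.05 per test and on any positive test counting:

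- about 16% to 24% for six tests at correlations 0.7 to 0.3, and 26.5% if independent;
- about 11% to 14% for three regions with one contrast;
- about 8% to 10% for a combined mask with two velocities.

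A reader might conclude that the plan has a 26% false-positive rate. The documents do not support that. The figure needs separate volumes, two tests per region, independence and an alpha that the plan does not give.

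This is a worthwhile improvement to a mechanistic aim. It does not affect the pleasantness analysis on which the trial was sized.

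**What to change.** In Data Analysis:

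1. Name one primary imaging contrast, for example the drug effect on slow minus fast, and state its alpha. The choice of contrast is the sponsor's; it needs to be fixed before the data are seen.
2. Define the search volume. Either apply one small volume correction over a combined OFC, STS and insula mask, or test the three regions separately with Holm.
3. If both velocities are to stay confirmatory, use Holm over all six tests.
4. State what result counts as support for Aim 2.
5. Label the remaining contrasts and the whole-brain search as exploratory.

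No new data or participants are needed. The cost is wording and a stricter threshold: under Holm the smallest p-value faces 0.0167 with three tests or 0.0083 with six, with the loss of power per region illustrated above. A combined mask also raises the voxel threshold, because a larger volume is searched; the documents do not allow that cost to be calculated.

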**Methods:**

**Design:** The study will use a 2-session within-subjects double blind design in which participants will receive MDMA or placebo in randomized order. Participants will vary in scores on the Autism Spectrum Quotient (ASQ). On each of two 4.5-hour sessions participants will first report to the Human Behavioral Pharmacology Laboratory suite for drug administration, and then they will be escorted to the MRI Research Center (MRIRC) for the fMRI scan. Subjective ratings will be obtained at regular intervals throughout the session and performance on the tasks, as well as neural measures of activation, will be obtained during the scans.

**Subjects:** 45 healthy volunteers (22 male, 23 female; age range 21-40 years) will participate in the experiment. Sample size was determined with a power analysis on preliminary data showing

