MDMA increases pleasantness ratings of touch ( $d=0.44$ ). Recruiting 45 subjects will provide greater than 80% power to detect an effect. Based on our previous rates of participants completing all four sessions after enrolling in the study, to recruit 45 subjects, we will need to consent 60 participants. Subjects will complete the Autism Spectrum Quotient (ASQ), and we will recruit individuals with a range of scores on the questionnaire, with 15 each from the 0-10 range, 10-20 range, and 20-32 range. Subjects with clinically significant ASD, as determined by our screening interviewers and the participants' responses to questions during the psychiatric screening interview will not be included in the study and will be referred for treatment. In particular, any participants who have difficulty understanding or complying with the study requirements will be ineligible. Subjects will also complete the Social Anxiety Questionnaire (Caballo et al, 2012). All participants will be recruited without regard to race, religion or ethnicity through posters, advertisements and word-of-mouth referrals. Candidates will be screened in accordance with our general screening protocol, approved by the IRB under Protocol #13681B, which includes a physical, EKG, psychiatric screening interview and detailed drug use history questionnaire. We will enroll individuals who report having used ecstasy at least 4 times but not more than 40 times, with no adverse responses. Because MDMA will be administered as part of the study, the following populations are excluded for safety reasons: Individuals with a BMI  $<19$  or  $>30$ , or weighing under 130 lbs, as this alters dosing requirements; Individuals with high blood pressure, abnormal EKG, any medical condition requiring regular medication, or any other medical contraindication to MDMA administration as determined by our study physician; Individuals with a current (within the last year) DSM-IV Axis I diagnosis, excluding non-treatment seeking drug abuse; Individuals with a history of dependence on stimulant drugs; Women who are pregnant. Smokers smoking more than 25 cigarettes per week will also be excluded, to avoid confounding the effects of nicotine withdrawal with the effects of the study drugs/procedures, as participants will not be allowed to smoke during the sessions. The self-report questionnaires we use require fluency in English, and have not been translated and validated in other languages, thus individuals with less than a high-school education or those not fluent in English will be excluded.

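### No dose model in this two-session crossover has a session or order term, and balancing of order within ASQ ranges is not described

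*Combined protocol and SAP*

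**What the plan says.** The Design paragraph under Methods states: "The study will use a 2-session within-subjects double blind design in which participants will receive MDMA or placebo in randomized order". It does not say how order is generated, and no section describes blocking, counterbalancing or stratifying order by ASQ range.

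The Data Analysis section describes four analyses involving dose:

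- **Pleasantness of touch:** "Change scores will be computed for ratings of pleasantness of affective touch (MDMA-placebo"). The Affective Touch Task section identifies the outcome: "The primary behavioral ratings in this task are the ratings of pleasantness of the brushing".
- **Oxytocin and subjective ratings:** "Oxytocin levels and subjective ratings will be compared with ANOVAs with ASQ (low, medium, high) as a between-subjects factor", with dose as the within-subject factor.
- **Subjective and mood effects:** a repeated-measures ANOVA "with AQ (low, medium, high) as a between-subjects factor, and dose (placebo or MDMA) and time as within-subjects factors".
- **Touch-task imaging:** "We will use repeated-measures ANOVAs to assess significant effects of drug (placebo versus MDMA) on each of the two brush velocities".

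Session, period, order and sequence appear in none of them. The time factor does not stand in for session. The Procedure section says "Participants will then complete Time 1 measures of subjective mood and drug effects, and complete these same measures periodically throughout the study", and the Timeline numbers these points Time 1 to Time 5 within a single session.

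On sample size, the Subjects paragraph says: "Recruiting 45 subjects will provide greater than 80% power to detect an effect".

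**The concern.** In a two-period crossover, a general shift between the first and second session enters each participant's MDMA-minus-placebo difference with a sign set by order. A shift is plausible here. Pleasantness is rated in the scanner, session 1 is the first study scan, and the Procedure section describes no practice scan or practice touch task. No document gives its size.

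Two harms follow, and they are largely alternatives.

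1. **Order close to even.** The shift adds to the error variance. Power falls, and the dose and ASQ-by-dose tests become conservative.
2. **Order split differently across ASQ ranges.** The shift is partly confounded with the group difference in MDMA response. Aim 1 depends on that comparison, and each range has only 15 people (12-14 according to the screening-measures section).

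**Working it through.** **Inputs.** From the Subjects paragraph: N = 45, d = 0.44, 15 per ASQ range. From the screening-measures section: 12-14 per range. Assumed, because not stated: two-sided α = 0.05; d is the mean paired difference over its SD; session shift π = 0.2, 0.3 or 0.5 SD of the paired difference; order by simple randomisation where so labelled.

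**The plan's own figure.** A paired t-test with noncentrality 0.44 × √45 = 2.95 on 44 df has power 82.3%. The claim of more than 80% reproduces, with about two points to spare.

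**Model.** For participant i, D = τ + sπ + e, where s = +1 if MDMA is second and −1 if first, SD(e) = 1 and τ = 0.44. Without an order term:

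- bias in the mean difference = π × (n MDMA-second − n MDMA-first)/N
- SD of D is about √(1 + π²), so effective d is about 0.44/√(1 + π²)

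Effective d is 0.44/1.020 = 0.431, 0.44/1.044 = 0.421 and 0.44/1.118 = 0.394 for the three shifts. By this formula power falls below 80% at about π = 0.25.

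**Power for the dose effect, d free of session effects (simulation):**

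| Shift (SD) | No term, 23:22 | No term, simple randomisation |
|---|---|---|
| 0.2 | 81.2% | 80.9% |
| 0.3 | 79.8% | 79.0% |
| 0.5 | 75.5% | 73.4% |

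The 23:22 column averages over which order has 23. With the term, power is about 82.2% at 23:22 and about 81.4% under simple randomisation, whatever the shift. At 0.5 SD the loss is 82.2 − 75.5 = 6.7 points, or 81.4 − 73.4 = 8.0 points.

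**Power if the SD behind d = 0.44 already contains the shift.** Planned power stays 82.3%. Removing the shift gives d = 0.44 × √(1 + π²) = 0.449, 0.459, 0.492, and on 43 df power becomes 83.7, 85.4 and 89.7%.

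**Type I error for dose at π = 0.5, no term:** 2.9% at 23:22; 5.0% averaged over simple randomisation.

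**Bias between ASQ ranges.** A range of n with k people receiving MDMA second has its mean difference moved by π(2k − n)/n. For 10:5 this is +π/3 and for 5:10 it is −π/3. The gap is 0.67π, that is 0.13, 0.20 and 0.33 SD.

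**Chance of that imbalance.** With k ~ Bin(15, 0.5) in each range, P(|k high − k low| ≥ 5) = 9.9%. The probability of a bias of at least 0.67π is 15.2% for n = 12 (difference ≥ 4), 7.6% for n = 13 (≥ 5) and 8.7% for n = 14 (≥ 5).

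**ASQ-by-dose type I error, three ranges of 15, no term:**

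| MDMA-second counts by range | π = 0.3 | π = 0.5 |
|---|---|---|
| 7 / 8 / 8 | 3.9% | 2.5% |
| 5 / 8 / 10 | 5.8% | 6.6% |
| 4 / 8 / 11 | 7.8% | 12.0% |
| averaged over simple randomisation | 5.0% | 5.1% |

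With the term it is about 5% throughout.

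**The case against.** The strongest reply is that no session shift has been shown. Its plausibility rests on the absence of a described practice session, and every size above is conditional on an assumption. That stands. A 0.5 SD shift would also exceed the whole planned MDMA effect of 0.44, so the figures at 0.5 SD are an upper bound, not an expectation. At 0.2 SD the loss is one point or less. At 0.1 SD under simple randomisation, power is about 81.9% without the term against about 81.4% with it, so the term costs slightly more than it saves. That small cost comes from uneven order and disappears once order is blocked.

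Confounding with ASQ is a chance event. A high-low difference of 7 or more, as in the 4/8/11 split, has probability 1.6% under simple randomisation, and average type I error is unaffected. This also stands. It limits the severity, but it does not help the one trial in which the split turns out uneven.

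Some analyses are partly protected. A constant shift cancels from dose-by-time in the mood model, and from drug-by-velocity, because both velocities occur within each session. It does not cancel from the dose main effect, from the drug effect at each velocity (which the plan names), or from ASQ-by-dose.

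Finally, the plan attaches no specific test to the change score, and imaging methods are partly deferred to cited papers. For imaging, therefore, the point is only that this document states no such term.

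**Conclusion.** The concern holds. None of the stated dose analyses accounts for session or order, and no balancing of order within ASQ ranges is described. Because order is randomised, the tests are valid on average. What is at risk is precision, and bias conditional on the order split that actually occurs.

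If d = 0.44 is free of session effects, the power loss is about 1 point or less for a 0.2 SD shift and 7-8 points for 0.5 SD; a shift of roughly 0.25-0.3 SD takes power below 80%. If the SD behind d = 0.44 already contains the shift, there is no shortfall against plan, but the term would raise power to between 83.7 and 89.7%. The comparison between ASQ ranges is the more exposed one: with 15 per range and simple randomisation there is about a 1 in 10 chance of a high-low bias of at least 0.67 times the shift.

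These figures rest on the assumed shift sizes, two-sided α = 0.05, d read as a paired effect size, and simple randomisation where stated. The change should be made because it is cheap and helps under either reading of d; the trial is not invalid without it.

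**What to change.** 1. In Data Analysis, add session number (1 or 2) as a fixed effect to the pleasantness, mood, oxytocin and second-level imaging models. In a model for the MDMA-minus-placebo difference, an additive order term is equivalent. Name the test applied to the pleasantness change score.
2. In Design, state how order is randomised, and randomise it in blocks within each ASQ range. With 15 per range the closest possible split is 8:7.
3. State the limit: the term corrects an additive session shift. It does not remove expectations carried over from the first drug received.

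The cost is analysis-plan wording, a stratified allocation list and one error degree of freedom. Crossing order fully with ASQ would cost three (45 − 3 = 42 falling to 45 − 6 = 39) and is not needed for an additive shift. No participants, visits or procedures change. Specifying the term in advance also removes a later choice between adjusted and unadjusted results.
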